2.1 Analysis Datasets and Baseline Comparisons

Data from all enrolled patients, regardless of whether or not they completed all protocol follow-up requirements, will be included for analysis. Baseline comparisons of patient characteristics and randomization stratification variables between intervention and control arms groups will be summarized as the mean; standard deviation; median; and 25th, 75th percentiles for continuous variables; and as counts and percentages for categorical variables. We will present baseline

Statistical Analysis Plan

characteristics and randomization stratification variables at both the patient and cluster levels. Cluster level summary data will be presented as means (standard deviations). All study objectives will be analyzed using intention-to-treat analyses.

2.2 Analysis Populations

The study population for primary and secondary analyses in ARTEMIS will start with all enrolled patients who survived the index MI hospitalization and did not withdraw from the study before hospital discharge. Since the intervention arm voucher provides copayment assistance for a generic (clopidogrel) or a brand (ticagrelor) P2Y₁₂ receptor inhibitor, we will conduct the primary endpoint analyses first among patients discharged on either clopidogrel or ticagrelor, and then repeat the analysis among all patients regardless of discharge P2Y₁₂ receptor inhibitor type.

2.3 Accounting for Hospital Clustering: Marginal vs. Conditional Modelling Approaches for Binary Endpoints

There are two general approaches that account for within hospital correlation in a statistical model; they are 1) marginal or population-averaged model and 2) conditional or subject-specific model. These two approaches differ in interpretation of model estimates and the way that correlation of measurements are incorporated in the model. For example, under the marginal model, the exponentiated treatment coefficient represents the odds of an average patient in the treatment group to be persistent compared to an average patient in the control group. Under the conditional random-effects model, the exponentiated treatment coefficient represents the odds of persistence for a treated person compared to the same person if they were not treated. As stated in the protocol we will use population averaged methods as our primary approach to account for hospital clustering.

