ARTEMIS is a prospective cluster-randomized clinical trial that will evaluate whether patient copayment reduction significantly influences antiplatelet selection and long-term adherence. This study will also examine patient outcomes and the overall cost of care after AMI. After IRB approval, sites will be randomized to either the intervention or the control. Randomization will be stratified by annual site AMI volume and proportion of ticagrelor use using medians across potential sites as cut-offs for identifying high vs. low categories. Approximately 11,000 patients with STEMI or NSTEMI will be enrolled at approximately 300 hospitals.

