1.1 Primary Objectives

The co-primary objectives of ARTEMIS are the following:

To determine if patient copayment reduction leads to higher long-term persistence of any P2Y₁₂ receptor inhibitor at one year after discharge.

To determine if patient copayment reduction leads to lower risk of MACE (composite of death, AMI, and stroke) at one year after discharge.

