1.2 Secondary Objectives

To evaluate whether reducing patient copayments affects selection of P2Y₁₂ receptor inhibitor medication at discharge.

To assess the impact of copayment reduction on the total cost of health care for patients after AMI.

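### Section 2.2 runs both co-primary analyses first in patients discharged on clopidogrel or ticagrelor, a set formed after randomization, and no rule says whether that result or the all-patient result decides the trial

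*SAP*

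**What the plan says.** SAP section 2.2 defines a starting set: the study population "will start with all enrolled patients who survived the index MI hospitalization and did not withdraw from the study before hospital discharge". It then narrows that set for the co-primary endpoints: "we will conduct the primary endpoint analyses first among patients discharged on either clopidogrel or ticagrelor, and then repeat the analysis among all patients", whatever the discharge agent. The reason given is that the voucher helps pay for these two drugs.

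Section 2.1 says something different. "Data from all enrolled patients, regardless of whether or not they completed all protocol follow-up requirements, will be included for analysis", and "All study objectives will be analyzed using intention-to-treat analyses".

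The SAP treats discharge drug as something the intervention may change. Its opening paragraph says the trial "will evaluate whether patient copayment reduction significantly influences antiplatelet selection and long-term adherence". The first secondary objective (section 1.2) is "To evaluate whether reducing patient copayments affects selection of" P2Y12 inhibitor at discharge. Section 4.1 tests discharge drug type as an endpoint, in all patients. Section 1.4 attributes part of the expected MACE benefit to the choice of a more potent agent.

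Sites are randomized after IRB approval, so the discharge drug is always chosen after allocation. Section 2 lists lack of blinding among the items to be reported.

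**The concern.** A randomized comparison is protected only if membership of the analysis set does not depend on what happens after allocation. Here membership depends on the discharge drug. If the voucher leads some intervention patients to leave on a covered drug when they would otherwise have left on another, those patients enter the intervention side of the restricted set. Their usual-care counterparts are left out. If they also differ in prognosis, the arms differ even when the intervention has no effect on the endpoint.

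The second problem needs no bias at all. Each co-primary endpoint is analysed in two populations, section 2 calls any p-value below 0.05 significant, and no text ranks the two. The table shells do not settle it: Table 3a has one row for MACE, Table 4a has one row for non-persistence to any P2Y12 inhibitor, and neither names a population. If the two results disagree, the plan does not say which one is the trial's answer.

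**Working it through.** **1. The SAP's own sample-size figures.** Inputs (section 1.4): 11,000 patients, 300 sites, mean cluster size m = 36.67, CV 0.65, 1:1 allocation, two-sided 0.05, continuity-corrected chi-square. Design effect = 1 + ((CV² + 1)·m − 1)·ICC.

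- Persistence, ICC 0.025: 1 + (1.4225 × 36.67 − 1) × 0.025 = 2.279. Effective N = 11,000 / 2.279 = 4,827, as stated. Power for 70% vs 74% is 86.5%.
- MACE, ICC 0.01: design effect 1.512, effective N 7,277 (stated 7,278). Power for 12.0% vs 9.84% is 83.1%.

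These figures reproduce. They use all 11,000 enrolled patients and make no allowance for removal by discharge drug.

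**2. Power if the restricted set decides.** The SAP gives no share discharged on other agents, so the share is assumed. The method is as in step 1, with N reduced.

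| Share removed (assumed) | Persistence power | MACE power |
|---|---|---|
| 0% | 86.5% | 83.1% |
| 5% | 85.7% | 81.8% |
| 10% | 84.9% | 80.3% |
| 15% | 83.9% | 78.7% |
| 20% | 82.9% | 77.0% |

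**3. Bias with no true effect, before adjustment.** Let R be the overall rate, equal in both arms. Let q be the share of an arm on an uncovered drug and x the event rate among those patients. The rate in the restricted set is (R − q·x)/(1 − q). R = 12% and 70% are the SAP's control-group assumptions; q and x are assumed here.

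| Endpoint | q, usual care → intervention | x | Usual care | Intervention | Difference (points) |
|---|---|---|---|---|---|
| MACE | 20% → 20% | 6% | 13.50% | 13.50% | 0 |
| MACE | 20% → 10% | 12% | 12.00% | 12.00% | 0 |
| MACE | 5% → 4% | 8% | 12.21% | 12.17% | −0.04 |
| MACE | 10% → 5% | 8% | 12.44% | 12.21% | −0.23 |
| MACE | 15% → 8% | 6% | 13.06% | 12.52% | −0.54 |
| MACE | 20% → 10% | 6% | 13.50% | 12.67% | −0.83 |
| MACE | 20% → 10% | 18% | 10.50% | 11.33% | +0.83 |
| Persistence | 10% → 5% | 76% | 69.33% | 69.68% | +0.35 |
| Persistence | 20% → 10% | 80% | 67.50% | 68.89% | +1.39 |
| Persistence | 20% → 10% | 60% | 72.50% | 71.11% | −1.39 |

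Worked example, sixth row: (0.12 − 0.20 × 0.06)/0.80 = 13.50%, and (0.12 − 0.10 × 0.06)/0.90 = 12.67%.

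The first two rows show the conditions for no bias: nobody crosses the covered/uncovered boundary, or those who cross do not differ. The sign depends on whether the patients who cross do better or worse.

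**4. What the largest MACE shift would do to the test.** For 20% → 10% with x = 6%, N = 11,000 × 0.85 = 9,350. The design effect is 1.433 and the effective N 6,523. The standard error of the difference is √(4 × 0.1308 × 0.8692 / 6,523) = 0.835 points. The shift is therefore about one standard error, and an unadjusted two-sided 5% test would reject about 17% of the time. For 10% → 5% with x = 8%, the same steps give about 6%.

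**The case against.** Several counter-arguments have force.

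- **Most of the drug selection the SAP has in view stays inside the set.** Both covered drugs qualify, sites must stock both, and randomization is stratified by ticagrelor use. A move between clopidogrel and ticagrelor takes nobody across the boundary. This stands. Bias needs movement into or out of the covered pair.
- **The SAP does not say that the voucher moves patients across that boundary.** The objective is to evaluate whether it affects selection. This stands, so bias is a possibility that the design leaves open and not an established fact.
- **The primary models adjust for much.** They include age, sex, race, payor, region, the site strata and a propensity score with a long variable list (sections 8.3.1 and 8.3.2). Adjustment may remove the part of the prognostic difference that these variables explain. It cannot be relied on for the rest.
- **The all-patient analysis is already prespecified.** True, but only as a repeat, with no stated precedence.
- **The restriction targets patients the voucher could help.** That is a fair supportive question. It does not justify removing usual-care patients according to a choice made without the voucher.
- **Discharge alive is also a post-randomization condition.** True, so the proposed population is not strict intention-to-treat either. It is, however, the starting set that section 2.2 already adopts, it does not depend on the discharge drug, and both endpoints are counted from discharge.

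A reader might also infer a conflict with section 1.1, "To determine if patient copayment reduction leads to higher long-term persistence of any" P2Y12 inhibitor. The text does not support that. The word defines the endpoint, so that a patient who switches still counts as persistent. Section 4.2 contrasts it with persistence to the initial drug. It does not say who is analysed.

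**Conclusion.** The point holds on two grounds that need no assumption. The population analysed first is defined by a post-randomization choice that the trial tests as an outcome, which contradicts section 2.1. And no rule says which of the two populations decides either co-primary endpoint.

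The bias is conditional and its size cannot be known from the SAP. Under assumed falls in uncovered use of up to 20% to 10%, with no true effect and before adjustment, it runs from zero to about 0.8 points for MACE, or 39% of the planned 2.16 (0.83/2.16). For persistence it runs from zero to about 1.4 points, or 35% of the 4-point target (1.39/4). Either sign is possible. The upper ends are corner cases, and a small shift such as 5% to 4% gives almost nothing.

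Three stronger readings go beyond the text. One is that the bias favours the intervention: the direction depends on who crosses the boundary, and the SAP is silent on this. Another is that the restricted analysis is formally ranked as primary: section 2.2 orders the two analyses but does not rank them. The third is that covariate adjustment is useless here: it may help, but cannot be counted on for unmeasured differences.

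The power figures likewise rest on an assumed excluded share and on the SAP's 1:1 allocation, which section 2 says was later changed to 2:1.

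**What to change.** In section 2.2, name one deciding population for both co-primary endpoints: all enrolled patients discharged alive and not withdrawn before discharge, regardless of discharge P2Y12 inhibitor. Label the clopidogrel/ticagrelor analysis as supportive and state that it cannot decide the trial. Report by arm the number and share of patients it excludes. Put the population name in the titles of Tables 3a and 4a. Reword section 2.1 so that its all-enrolled and intention-to-treat sentences agree with the population named in section 2.2, including the conditions on survival and withdrawal before discharge.

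The cost is wording only, since both analyses are already planned, and the deciding analysis then starts from the full enrolment on which the power calculation rests. The downside is slight dilution of the effect by patients on an agent that the voucher does not cover.

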2.4 Missing Data

Operational efforts will be made to minimize missing data at baseline and during follow-up. During the enrollment phase, baseline data will be reviewed on a monthly basis and sites will be notified regarding any data quality concerns. Study personnel will confirm that missing data cannot be obtained. Follow-up data will be regularly reviewed after 50% of patients reach 3 months post-discharge.

We will impute socioeconomic variables, lab values, and weight to age, gender, and race specific modes for categorical variables and medians for continuous variables. Medical history, home medications, admission features, and in-hospital events will be imputed to the mode.

3 Primary Endpoints

3.1 Non-persistence with antiplatelet therapy at 1 year

The co-primary endpoint of long-term non-persistence will be assessed using patient-reported medication non-persistence. Permanent and temporary discontinuation of a P2Y₁₂ receptor inhibitor will be queried at each follow-up interview. For patients with missing patient-reported medication information, pharmacy fill data will be used to ascertain persistence. Patients who have continued P2Y₁₂ receptor inhibitor use at one year from discharge with less than 30

Statistical Analysis Plan

continuous days of interruption will be considered persistent. We will use the last observation carried forward (LOCF) method for patients who died before one year or had missing 1 year P2Y₁₂ status.

The co-primary objective determines whether patient copayment reduction leads to higher long-term persistence with antiplatelet therapy at one year. The study endpoint for this objective is the proportion of patients at one year who had an interruption ≥ 30 days of P2Y₁₂ receptor inhibitor. The primary analysis will be a logistic regression model with parameters estimated using generalized estimating equations (GEE) to account for within hospital clustering and adjustment for selected patient characteristics (Section 8.3.1) which includes a propensity score for intervention (Section 8.3.2). The propensity score will be estimated using a logistic regression model for intervention group. Categorical variables will be included as sets of indicator variables. Continuous variables will be included assuming a simple linear relationship. Balance of covariates between intervention and usual care arms will be assessed using standardized differences as recommended by Austin [6]. We will assess functional form and possible transformations of the propensity score to be included in the outcome model. Cluster heterogeneity will be quantified using ICCs calculated from unadjusted and adjusted models. We will calculate the ICCs across all hospitals and also by treatment group.

After Steering Committee consensus, the randomization scheme was changed from 1:1 to 2:1 Usual Care vs. Intervention effective November 16, 2015. Randomization schema was added as a covariate for adjustment as shown in Section 8.3.1 and to the propensity model as shown in Section 8.3.2.

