1.4 Sample Size Justification

The proposed sample size has been determined to provide adequate statistical power for the co-primary study objectives related to the copayment reduction intervention. The co-primary objective determines whether patient copayment reduction leads to greater persistence to P2Y₁₂ receptor inhibitor therapy at one year after hospital discharge. The hypothesis underlying this objective is that reducing patient copayment in a contemporary population of AMI patients will result in a significant increase in persistence to P2Y₁₂ receptor inhibitor therapy at one year, when compared with usual care. An increase of 4% in the persistence to P2Y₁₂ receptor inhibitor therapy would be considered a clinically important difference[1]. To achieve this objective with a patient-level randomization design, a sample size of 5392 patients would provide greater than 90% power with a two-sided Type I error rate of 0.05. A sample size of 4622 patients would provide greater than 85% power under the same assumptions. These power calculations are based on the assumption that the expected one-year persistence rate in the control group is 70%[1]. These calculations are based on the two group continuity corrected chi-square test statistic and assume that all observations are independently distributed. However, the sample size needs to be adjusted due to the cluster randomized design. We have applied the method described by Eldridge et al. [2] which accounts for the coefficient of variation (CV) of cluster

Statistical Analysis Plan

size and the intra-cluster correlation (ICC). Based on prior multicenter studies, we anticipate an ICC for this endpoint of approximately 0.025. Assuming a total of 300 sites randomized (1:1) with an average sample size of 36.67 patients per site and a CV of 0.65 would yield a design effect of approximately 2.28. The CV of 0.65 has been suggested by others and can be guided by providing minimum and maximum enrollment at the site level [2]. Therefore, a total sample size of 11,000 patients enrolled at 300 sites would result in an effective sample size of 4827 and be sufficient to provide between 85% and 90% power to detect an absolute 4% difference between treatment groups in the cluster randomized design.

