Patient-reported persistence to antiplatelet therapy will be validated using pharmacy records that will be collected on a subset of the overall study population. The assumed standard deviation of 0.25 (for the proportion of days covered) is based on a recent randomized clinical trial to assess an intervention designed to improve adherence [4]. Assuming 1:1 randomization and a two-sided Type I error rate of 0.05, a sample size calculation based on the two-sample t-test suggests that a total sample size of 1644 patients will yield 90% and a total sample size of 2034 will yield 95% power. A random sample of 2400 patients from the 300 sites randomized with a CV of 0.25 and an ICC of 0.025 would yield a design effect of approximately 1.26. The resulting effective sample size of 2021 patients would yield approximately 95% power to detect a difference of 4% between the patient copayment reduction intervention and control groups. The target sample size of 2500 patients with pharmacy records allows for 4% missing data due to records that are not available.

2. General Considerations for Data Analysis

We will include a detailed flow diagram showing the number of participants' eligible, number of subjects randomized to Copayment Intervention and Usual Care arms, numbers of subjects lost to follow-up or excluded from analyses, and the number of subjects analyzed for the key study endpoints. Additionally, we will describe the number of clinical sites in Copayment Intervention and Usual Care arms including the mean (median, range) for key study elements by site. Key elements will include the following items: descriptions of participants, interventions, objectives, outcomes, and sample size justification; and details about the randomization procedure, factors used to stratify randomization, (lack of) blinding, statistical methods, participant flow, dates of recruitment, baseline data by individuals and by cluster, numbers analyzed, outcomes and estimation, adverse events, and a discussion. These elements are based on the CONSORT statement for cluster randomized studies [5].

After Steering Committee consensus, the randomization scheme was changed from 1:1 to 2:1 Usual Care vs. Intervention effective November 16, 2015. Randomization schema was added below as a covariate for adjustment.

All analyses will be conducted using SAS version 9.4 or higher software. All tests will be two-sided and a p-value of <0.05 will be considered statistically significant.

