3.2 MACE

The primary study objective evaluates whether patient copayment reduction leads to lower risk of MACE at one year. MACE is defined as the composite of all-cause death, recurrent myocardial infarction, and stroke. Follow-up will be censored at time of study withdrawal or last known alive. The time-to-first MACE event up to one year post-discharge will be compared between intervention and control arms. Cumulative incidence rates will be presented as Kaplan-Meier curves and in tables for 30 days, 6 months, and 1 year post-discharge. The primary analysis will be a Cox proportional hazards model accounting for within hospital clustering using robust standard errors and adjustment for selected patient characteristics (Section 8.3.1) which includes a propensity score for intervention. We will use the same propensity score described in section 3.1. Cluster heterogeneity will be quantified using ICCs calculated from unadjusted and adjusted models. We will calculate the ICCs across all hospitals and also by treatment group.

After Steering Committee consensus, the randomization scheme was changed from 1:1 to 2:1 Usual Care vs. Intervention effective November 16, 2015. Randomization schema was added as a covariate for adjustment as shown in Section 8.3.1 and to the propensity model as shown in Section 8.3.2.

4. Secondary Endpoints

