8.3 Appendix: List of Adjustment Variables

8.3.1 Adjustment Variables for Primary Models

Variable	Variable Type
Intervention	Yes/no
Randomization scheme	Categorical (2:1 vs. 1:1 scheme)
Interaction* between intervention and randomization scheme	Categorical
Site MI volume	Categorical (high vs. low)
Site % Ticagrelor use	Categorical (high vs. low)
Age	Continuous
Male gender	Yes/no
Race	Categorical (white vs. nonwhite)
Insurance Payors	Categorical (private vs. non-private)
Region	Categorical (Northeast, West, South, vs. Midwest)
Propensity for intervention	Continuous

*We will test for significant interaction and will drop if the interaction term is not significant.

Statistical Analysis Plan

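### Both co-primary models adjust for a fitted propensity score but make no variance allowance for having estimated it, so the reported intervals can be too wide and some power is given up

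*SAP*

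**What the plan says.** SAP 3.1 analyses one-year non-persistence by logistic regression with GEE and "adjustment for selected patient characteristics (Section 8.3.1) which includes a propensity score for intervention (Section 8.3.2"). On the score it says: "The propensity score will be estimated using a logistic regression model for intervention group". SAP 3.2 analyses MACE by Cox regression with hospital-robust standard errors and the same adjustment: "We will use the same propensity score described in section 3.1".

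The list in 8.3.1 enters these terms directly: randomization scheme (and its interaction with intervention, if significant), the two site strata, age, sex, race, payor and region. It adds one continuous term, "Propensity for intervention". The list in 8.3.2 holds about 40 further variables that reach the outcome models only through that term. Among them are prior MI, heart failure, dialysis, diabetes, creatinine clearance, cardiogenic shock, PCI, home P2Y₁₂ inhibitor, financial hardship, missed doses and several site features.

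Neither 3.1 nor 3.2 mentions a bootstrap, stacked estimating equations or any other step for the uncertainty in the score. Significance is set in Section 2: "All tests will be two-sided and a p-value of <0.05 will be considered statistically significant".

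**The concern.** A fitted score is not an ordinary covariate. Its coefficients are tuned to the imbalance seen between the arms of this trial. Adjusting for it therefore removes the part of the treatment estimate's error that comes from imbalance in all the score's variables. The residuals still carry the outcome variation that those variables explain, because a single score weighted by imbalance is a poor predictor of outcome. A GEE or robust Cox standard error built from these residuals takes the score as given and misses the precision gained.

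The affected quantities are the adjusted odds ratio and hazard ratio, with their confidence intervals and p-values, in Tables 3a and 4a. The error is conservative: intervals too wide, and a true benefit somewhat more likely to be missed.

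**Working it through.** **1. The plan's own figures reproduce.** They rest on an unadjusted test: "These calculations are based on the two group continuity corrected chi-square test statistic". The "expected one-year persistence rate in the control group is 70" per cent, and the target is an "absolute 4% difference between treatment groups in the cluster randomized design". Per arm, n₀ = [1.96√(2p̄q̄) + z_β√(p₁q₁+p₂q₂)]²/d², then n = (n₀/4)[1+√(1+4/(n₀d))]².

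- Persistence (0.70 v 0.74, 90% power): n₀ = 2645.8, n = 2696, total 5392.
- MACE (0.12 v 0.0984, 80% power): n₀ = 3271.7, n = 3364, total 6728.
- The other two totals, 4622 and 7670, also reproduce.
- Design effect 1 + [(0.65²+1)×36.67 − 1]×ICC is 1 + 51.16×0.025 = 2.279 for persistence and 1 + 51.16×0.01 = 1.512 for MACE.
- Effective N is 11,000/2.279 = 4827 and 11,000/1.512 ≈ 7277 (SAP: 7278). Power is 86.5% and 83.1%, inside the stated ranges.

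**2. Mechanism, linear case.** Let P̂ be the fitted linear score for arm Z on covariates X. Z − P̂ is orthogonal to P̂, so the part of Z left after adjusting for P̂ is Z − P̂. The same part is left after adjusting for all of X. The treatment coefficient is therefore identical in the two models, but the residual variance is not: only the model with X removes what X explains. In the SAP the score is logistic, and site volume, site ticagrelor use and region are outside it, so the identity is only approximate. The size has to be simulated.

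**3. Simulation at the SAP's design.** From the SAP: 300 sites, mean 36.67 patients, CV 0.65, the stated event rates, effects and outcome ICCs. Assumed, because the SAP gives none: 40 patient and 5 site covariates; overall AUC 0.63–0.79; 25% or 75% of prognostic strength in a directly entered covariate; covariate ICC 0, 0.03 or 0.10; 1:1 allocation. There were 800–1500 runs per scenario, with Monte Carlo error of about 2% on SE ratios and 1 point on power.

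Results under the planned effect, covariate ICC 0.03, 25% of strength entered directly:

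| Endpoint (AUC) | SE/true SD, no score | SE/true SD, SAP model | Power, SAP model | Same estimator, true SD | Direct entry |
|---|---|---|---|---|---|
| Persistence (0.63) | 1.00 | 1.02 | 89.2% | 90.1% | 90.2% |
| Persistence (0.70) | 0.99 | 1.04 | 90.4% | 91.5% | 92.7% |
| Persistence (0.755) | 0.99 | 1.09 | 91.5% | 94.5% | 95.0% |
| MACE (0.72) | 1.05 | 1.11 | 85.3% | 89.7% | 87.8% |
| MACE (0.785) | 1.03 | 1.13 | 84.2% | 90.6% | 90.4% |

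- Weak covariates for MACE (AUC 0.65): power 86.1%, against 87.1% with direct entry.
- Covariate ICC 0.10: SE/SD up to 1.13 (persistence) and 1.18 (MACE). Power was 88.4% against 92.4%, and 81.6% against 88.7%.
- 75% of strength entered directly: the score raises SE/SD only from 1.01 to 1.02 (persistence) and from 1.05 to 1.07 (MACE). Power was 91.7% against 93.0%, and 87.1% against 89.0%.
- Type I error of the SAP model over all scenarios: 1.9% to 4.9%.

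**4. Mixed allocation and the bootstrap.** A logistic simulation mixing 1:1 and 2:1 sites (400 runs per scenario) gave SE/SD of 1.06 at covariate ICC 0.04 and 1.11 at 0.08 with strong covariates, and 0.99 with weaker ones. A hospital bootstrap that refits the score matched the true SD to about 1% (0.0675 v 0.0670; 0.0683 v 0.0675).

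**The case against.** The best defence has four parts.

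- **No stated figure is wrong.** The sample size claims no gain from covariates, type I error is not inflated, and simulated power stays inside or above the planned ranges. This stands. A reader might infer that the trial is underpowered against its own plan; the calculations do not show that. Power is lost only against a better variance or a different model, and it stayed within about 3 points of the same model without the score, except where it was higher.
- **The score has a purpose.** A reader might infer that under site randomization it records chance imbalance alone and could be dropped. That does not follow. Patients consent and enrol after unblinded sites are assigned. The first primary analysis (2.2) is restricted by discharge agent, a choice that 4.1 tests as an effect of the intervention. A broad score may guard against differential enrolment. This argues for keeping the score, not for leaving its standard error uncorrected.
- **The main predictors may already be in the model.** It is tempting to say that the strongest risk factors enter only through the score. The SAP ranks none, and age, payor, region and the site strata enter directly. If most prognostic strength lies there, the score adds only 1–2% to the standard error.
- **Not all the excess width comes from the score.** For MACE the model without it already had SE/SD of 1.03–1.07. The direct-entry comparison is also slightly flattering: for persistence its uncorrected robust test rejected 5.5–6.2% of the time under the null. Direct entry moves the target as well, because odds and hazard ratios change when prognostic covariates are added (mean log odds ratio −0.239 against −0.206 at AUC 0.755).

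Unadjusted ratios with intervals are planned beside the adjusted ones, which helps a reader but does not correct the primary interval. That the score is handled as known is an inference from the model list and the silence on variance. It is nevertheless what the specified procedures do as written.

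**Conclusion.** The point holds as a conservative error in the reported precision of both co-primary effects. If the score-only variables are prognostic, standard errors are too wide by roughly 0–10% at low covariate clustering, and by up to about 10–18% with higher clustering or strong covariates. For MACE, some 3–7% of that is present without the score. Type I error is at or below 5%. The cost is about 1–7 points of power relative to a corrected variance or direct entry.

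These sizes rest on an assumed AUC of 0.63–0.79 and covariate ICC of 0–0.10. With weak covariates the effect is within simulation error. The main simulation used 1:1 allocation; the mixed-allocation runs agree in direction where covariates are strong. MACE has the thinner margin (83.1% planned power), so a few points matter more there. Validity is not at risk, but the intervals can be put right cheaply and should be.

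**What to change.** Keep the score-adjusted estimator in 3.1 and 3.2. Add that confidence intervals and p-values come from a bootstrap that resamples whole hospitals within randomization scheme and arm, refitting the propensity score and then the outcome model in each resample. A variance from stacked estimating equations for the score and outcome models, clustered by hospital, is an equivalent choice. State the number of resamples, the seed and the interval type, and fix the functional form of the score beforehand, since 3.1 leaves it to be assessed.

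Direct entry of a fixed list of pre-enrolment prognostic variables from 8.3.2, with small-sample-corrected robust standard errors, may be added as a sensitivity analysis. It need not replace the score.

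The cost is a few sentences in the SAP and more computing, with no new data. The trade-off is that the intervals lose their conservative margin.
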